Protocol Title: Addressing Cervical Cancer Disparity in South Florida: CBPR in Action Version Date: 2/4/16 NCT#02202109

- 1) **Protocol Title** Addressing Cervical Cancer Disparity in South Florida: CBPR in Action
- 2) **Principal Investigator** [name], MPH
- 3) **Sub-investigator** [name], MPH
- 4) **Study Contact** [name], MBA
- 5) Study Personnel (Listed on IRB7)
- 6) **IRB Review History**

N/A

7) **Objectives**

The study entitled "Health in Your Hands" will test the significance of community health worker participation by comparing Human Papilloma Virus (HPV) self-sampling provided by a community health worker and HPV self-sampling provided by mail. The study will enroll 700 participants in communities characterized by health disparities and lack of access to the formal healthcare system, such as Little Haiti, Hialeah, and South Dade.

8) Background*

In Miami, Florida, cervical cancer is a particular problem for Haitian and Caribbean Hispanic women. When compared to other racial/ethnic minority and immigrant groups in the Miami metropolitan area, Haitian and Hispanic women contribute disproportionately to cervical cancer incidence, morbidity and mortality, largely as a function of their underutilization of Pap smear screening. They do not undergo Pap smear screening for a myriad of reasons, including, but not limited to: poverty; language difficulties; limited access to health care; lack of knowledge about cancer and the importance of early detection; cancer fatalism or the belief that cancer implies death; and, cultural norms about health and disease prevention. The proposed project aims to overcome such barriers.

With funding from the National Cancer Institute, we have documented the prevalence of lifetime and routine Pap smear among women living in our communities of interest. Between March and May 2011, the community health workers approached approximately 200 women from various community venues across Little Haiti, Hialeah and West Perrine including Laundromats, health clinics, and churches. Of the participants, 71% reported having at least one Pap smear in their life. Of those with a history of screening (n=143), only 80% reported having a least one Pap smear in the past three years as recommended by national guidelines. There is not a direct comparison for our data, though in relation to national averages and data, the women in our sample appear to be under-screened.

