Following this data, a pilot study was conducted (funded by UM Sylvester and the University of Miami Institute for Women's Health) to examine whether Haitian women consider self-sampling a culturally-acceptable alternative to the Pap smear. A total of 250 women agreed to participate in

the study, which involved cervical self-sampling with the POI/NIH device (essentially a long q-tip with a protective sheath), as well as, completing a detailed survey. Findings indicate that acceptability of the device is high, that the majority of women prefer the self-sampler to the traditional, physician speculum exam and find it easy and comfortable to use. In addition to such positive results, this pilot study helped to establish the infrastructure necessary for successfully carrying out the proposed study.

9) Inclusion and Exclusion Criteria

Rational for inclusion/exclusion criteria: our target population is ethnic minority females aged 30-65 living in one of the three target communities who have not been screened for cervical cancer in the past three years (as per recent guidelines).

To be eligible women must be:

- Haitian, Hispanic, or African American
- ages 30-65 years
- report not having had a pap smear in the last three years
- live in the cities of Miami/Little Haiti, Hialeah or unincorporated Southern Miami-Dade

EXCLUSION CRITERIA:

Women will not be included in the study if they:

- report having had a hysterectomy
- have a history of cervical cancer
- plan to move outside of Miami-Dade county during the next six months
- are enrolled in any other cancer prevention/outreach related study

The study will exclude:

- Adults unable to consent
- Individuals who are not yet adults (infants, children, teenagers)
- Pregnant women
- Prisoners

10) Number of Subjects

700

11) Study-Wide Recruitment Methods

Participants will be recruited to participate in the study primarily through the efforts of Community Health Workers (CHWs), who are indigenous to the area, employed by our community partners and certified to conduct research by the University of Miami (UM) Institutional Review Board (IRB). The CHWs are not UM employees but are CITI-certified and are from either the Health

Choice Network, which includes the Citrus Health Network and Community Health of South Florida, Inc. (CHI), and the Center for Haitian Studies (CHS).

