Our primary endpoint is a returned HPV self-sampler kit. We have several planned subgroup analysis to help us understand if our intervention was more effective among certain population sub-groups. We therefore propose to examine whether the intervention was more efficacious among women with lower levels of educational attainment and those who are uninsured/underinsured. We consider all these analysis to be hypothesis generating, rather than hypothesis testing, given limited power. We also plan to examine several secondary endpoints, including: a) Access to care (health insurance, having a usual source of care, and visit to provider in six months). These would be analyzed as binary variables and would help explore if HPV self-sampling led to a decrease in access. b) Cervical cancer knowledge to help determine study fidelity. This is a continuous variable based on summed number of correct answers. c) Knowledge of test results and, for those with an abnormal screen, the proportion of women in each group who received appropriate initial follow-up within 30 days of the abnormal screen d) Acceptability of screening delivery.

14) **Procedures Involved***

Determination of eligibility The CHWs will screen potential participants for eligibility by asking whether they are 1) Haitian, Hispanic or African American, 2) 30-65 years of age or older, 3) have not had a Pap smear in the past three years, 4) has not had a hysterectomy, 5) has not been enrolled in a similar study (e.g. SUCCESS), 6) is not pregnant, 7) will not move in the next 6 months. For those women who screen potentially eligible, the CHW will further describe the study. Potential participants will be told that we are conducting a research study to determine the best method to increase rates of cervical cancer screening among women in their community. They will be told that the study will involve a brief education session about cervical cancer prevention and treatment, as well as instructions on how to use the HPV self-sampler we will be providing them with.

- Women who decline participation: For women who are potentially eligible but were not interested in participating, the brief demographic information collected during the eligibility screen (age, ethnicity) will be kept without any identifiable information. This data will be used to compare responders versus non-responders.

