- Women who agree to participate: The CHW will obtain signed informed consent from the women who are interested in participating.

Informed Consent and Intake Survey: After obtaining consent, the CHW will proceed with the intake interview. The intake interview will be conducted by our research assistants/community health educators (CHEs) to avoid introducing bias into our study design. Prior to beginning the intake survey, the CHE will first conduct another inclusion screen to verify that the potential participant still meets study inclusion criteria. The CHE will then re-explain the study to the potential participant and answer any questions she may have. If she is still agreeable to participating, the CHE will obtain signed informed consent. After obtaining consent, the CHE will proceed with the intake interview. The CHW will explain to participant that she will participate in two interviews 6 months apart, where each interview will take approximately 30 minutes to complete. This home interview will be conducted using laptop computers with wireless cards allowing access to the Research Electronic Data Capture (REDCap) web-based platform (see below). Backup paper copies will be available in case the CHE experiences difficulty accessing the web.

After completion of the intake survey, the participant will receive a \$25 gift card for their time and participation.

Randomization: Once participants complete the screening intake, they will be randomized into one of two possible interventions. Participants will be provided randomization information via phone by the CHW. Randomization will be done by REDCap, a secure web-based and HIPPA compliant system that allows to manage online surveys, database and reporting.

A custom allocation list has been created, which serves as a lookup table for deciding how to randomize subjects. Randomization of subjects will occur on the data collection form where your randomization field. After a subject has been randomized, it will become permanently locked and unmodifiable. The randomization field will always be locked and unmodifiable both before and after randomization has occurred for a subject. When the user randomizes the subject, REDCap will check the allocation table and assign that subject's randomization field value, which will be derived from the next match in the table based upon the criteria. In this case, it will simply provide the subject with the very next value in the allocation table.

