Protocol Title: Addressing Cervical Cancer Disparity in South Florida: CBPR in Action Version Date: 2/2/17 NCT#02202109

Statistical Analysis

Baseline characteristics were compared across the two study arms using chi-square tests (categorical data) and t-tests (continuous data). Crude differences in proportion of women screened by study arm (overall and stratified by neighborhood site) were tested using chi-square tests. We then modeled the association between sociodemographic variables and screening completion using univariate and multivariable logistic regression analyses. We included neighborhood site, age, income, insurance status, education, Pap history, marital status and citizenship status as covariates in the multivariable analysis. Race/ethnicity was not analyzed as it was highly collinear with site (e.g. all Haitians resided in Little Haiti). We report odds ratios (ORs) and corresponding 95% confidence intervals (CI) for the regression analyses. Secondary outcomes were analyzed using paired McNemar chi-square tests for the overall sample, and stratified by neighborhood site. All statistical tests were two-sided, with significance set at the p < 0.05 level. The data were analyzed using SAS 9.4 (SAS Institute Inc., Cary, NC, USA).

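### The SAP tests the arm effect separately in each neighbourhood site at an unadjusted p < 0.05, with no arm-by-site test and no hypothesis-generating label, so differing site p-values could be misread as differing effects.

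*SAP*

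**What the plan says.** The primary endpoint is binary (protocol section 13): "Our primary endpoint is a returned HPV self-sampler kit". The SAP analyses it as the proportion of women screened: "Crude differences in proportion of women screened by study arm (overall and stratified by neighborhood site) were tested using chi-square tests". One rule covers all tests: "All statistical tests were two-sided, with significance set at the p < 0.05 level". The secondary outcomes are analysed by paired McNemar tests, overall and again by site.

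The SAP describes no arm-by-site interaction, no homogeneity test and no multiplicity adjustment. Site appears in the multivariable logistic model only as one of the listed covariates.

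Protocol section 13 plans subgroup analyses by education and by insurance, and says of them: "We consider all these analysis to be hypothesis generating, rather than hypothesis testing, given limited power". Site is not among those subgroups, and the SAP does not repeat the label.

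**The concern.** Whether the arm effect varies by neighbourhood is a question about the difference between site effects. The plan offers only separate p-values to answer it. Each p-value reflects both the effect and the number of women in that site, so p-values can fall on either side of 0.05 when the effect is the same everywhere. With several tests at 0.05 each, there is also a raised chance that some site is significant when no effect exists.

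The stakes are practical. The SAP notes that race/ethnicity is highly collinear with site, so a chance difference between sites could be read as an ethnic difference in whether delivery by a community health worker helps. That could influence where such workers are deployed.

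**Working it through.** **Inputs from the documents**
- Total enrolment of 700 (protocol section 7): "The study will enroll 700 participants in communities characterized by health disparities".
- Three sites (protocol section 9): "living in one of the three target communities". The SAP's neighbourhood sites are taken to be these three.
- Two arms (protocol section 14): "they will be randomized into one of two possible interventions".
- Two-sided 0.05 for each test (SAP).

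**Assumptions, because neither document gives the figures**
- 1:1 allocation, so 350 women per arm.
- Three equal sites, so 350/3, or about 117, per arm per site.
- Overall power, varied below.

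The enrolment of 700 comes with no stated power or effect size, so there is no planned power figure to reproduce.

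**No effect in any site**

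P(at least one of three sites significant) = 1 − 0.95³ = 1 − 0.857 = 14.3%. Simulation gives 14–16%. In 11–13% of simulated trials a site is significant while the overall test is not.

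**The same effect in every site**

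Let d be the expected value of the overall z statistic: d = 1.960 + z(power). Each site has one third of the women, so its expected z is d/√3, and site power is s = Φ(d/√3 − 1.960). Then P(all three significant) = s³, P(none) = (1 − s)³, and P(mixed) = 1 − s³ − (1 − s)³.

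For 80% overall power: d = 1.960 + 0.842 = 2.802, d/√3 = 1.617 and s = Φ(−0.343) = 36.6%. All three: 0.366³ = 4.9%. None: 0.634³ = 25.5%. Mixed: 69.6%.

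| Overall power | Site power | None | All three | Mixed |
|---|---|---|---|---|
| 50% | 20% | 51% | 1% | 49% |
| 80% | 37% | 26% | 5% | 70% |
| 90% | 46% | 15% | 10% | 75% |
| 95% | 55% | 9% | 16% | 74% |
| 99% | 70% | 3% | 34% | 63% |
| 99.9% | 83% | 1% | 57% | 42% |

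A two-proportion calculation with lower-arm return rates from 30% to 80% gives nearly the same results. At a 70% lower-arm rate, the difference detectable with 80% power is about 9 points overall and about 15 points within one site.

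**Where the result stops holding**

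P(mixed) exceeds 50% only when site power is between 21% and 79%, which is overall power of about 52% to 99.8%. For a very large effect, 70% against 88% returned, simulation gives all three sites significant in 81% of trials and a mixed pattern in 19%.

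**Unequal sites**

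With sites of 400, 200 and 100 women, the mixed pattern appears in about 73–80% of trials at roughly 80–90% overall power.

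**A single arm-by-site test instead**

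Under a uniform effect, a 2-df homogeneity test at 0.05 wrongly flagged site dependence in 3.7–4.9% of simulated trials. Its power is limited. Suppose the effect is in one site only and is large enough for 80% power there. The noncentrality is then 2.802² × 2/3 = 5.23, and the test has about 52% power.

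**The case against.** The strongest reply is that no misreading is documented. The SAP never says that differing site p-values will be taken as effect modification, and the by-site results could simply be supplementary to the overall test. Section 13 already shows that the investigators regard subgroup results as hypothesis generating. All of this is fair. What stands is that the section 13 statement covers education and insurance only, while the SAP puts site tests under the same significance rule as the overall test and gives no method for comparing sites.

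A reader might infer more than the documents support:
- **That a uniform effect will usually look site-dependent.** This depends on overall power, which is not stated. It fails for small and for very large effects.
- **That chance site findings will be called significant.** This is a risk of about 14% for at least one site if there is no effect. It is not a certainty. Nor does it breach a stated error rate, because the SAP's 5% applies to each test and it claims no family-wise rate.
- **That the site strata are as small as the education and insurance strata.** No document gives the size of any of these strata.
- **That an arm-by-site term belongs in the secondary analyses too.** The McNemar tests are paired, are described for the overall sample, and have no arm term to which an interaction could attach.

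**Conclusion.** The point holds in a limited form. The SAP tests the arm difference by site at an unadjusted 0.05, has no test of whether that difference varies by site, and leaves the site results without the exploratory status given to the other subgroups. On the assumptions of 1:1 allocation and three equal sites, a uniform effect would produce a mixed pattern in about 70–75% of trials at 80–90% overall power. That falls to about 49% at 50% power and to about 19% for the very large effect shown. With no effect, at least one site is significant in about 14% of trials. The documents do not place the trial within this range. The overall arm comparison is not affected, so this is a correction to make in analysis and reporting and does not threaten the main result.

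**What to change.** 1. State that the overall arm comparison on the primary endpoint is the only confirmatory test.
2. For the primary endpoint, add one arm-by-site interaction (homogeneity) test. Report the arm difference in each site with a 95% confidence interval, labelled hypothesis generating and without significance claims.
3. Label the by-site McNemar results for the secondary outcomes hypothesis generating as well. Do not add an arm-by-site term there.

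The cost is a few sentences of SAP text and one extra model containing arm, site and their interaction. No new data are needed. The SAP is written in the past tense, but the change can still be made as a reanalysis or in reporting.

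There are two downsides. No site-level significance claim can be made. The interaction test also has limited power, so a non-significant result must not be reported as showing a uniform effect.

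If formal site tests are wanted, 0.05/3 = 0.0167 per site brings the family-wise error under no effect to 1 − (1 − 0.0167)³ = 4.9%. At 80–90% overall power, site power would fall from about 36–46% to about 21–30%. That would still not test whether the effect differs between sites.

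### The SAP's only method for secondary outcomes, a paired McNemar test with no study arm, does not fit the continuous knowledge score or by-group 30-day follow-up and yields no CHW-versus-mail estimate

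*SAP*

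**What the plan says.** The SAP covers the secondary outcomes in one sentence: "Secondary outcomes were analyzed using paired McNemar chi-square tests for the overall sample, and stratified by neighborhood site". Study arm does not appear in it. Arm does appear in the sentence on the primary outcome: "Crude differences in proportion of women screened by study arm (overall and stratified by neighborhood site) were tested using chi-square tests". Elsewhere in the SAP, t-tests are named only for baseline characteristics, and logistic regression, with the only confidence intervals, only for screening completion.

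Protocol section 13 lists four groups of secondary endpoints:

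- **Access to care**, made up of "health insurance, having a usual source of care, and visit to provider in six months". On these it says: "These would be analyzed as binary variables and would help explore if HPV self-sampling led to a decrease in access".
- **Cervical cancer knowledge**, which is there "to help determine study fidelity. This is a continuous variable based on summed number of correct answers".
- **Knowledge of test results** and, for women with an abnormal screen, "the proportion of women in each group who received appropriate initial follow-up within 30 days of the abnormal screen".
- **Acceptability** of the way screening was delivered.

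Section 7 gives the trial's purpose as "comparing Human Papilloma Virus (HPV) self-sampling provided by a community health worker and HPV self-sampling provided by mail". On timing, section 14 has the participant told that "she will participate in two interviews 6 months apart".

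**The concern.** McNemar's test compares two binary readings on the same unit. The two arms hold different women, so the only natural pair is intake versus six months within a woman. Run on the overall sample and by site, it is a before-after test pooled over arms. It cannot take a summed score for which no cut-point is given, and it cannot take an event that happens only after the study's own screen.

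If the plan is followed as written, the knowledge score and 30-day follow-up get no usable analysis, knowledge of results and acceptability have no clear method, and access is reported only as a time change without a control. A reader would learn nothing about how CHW and mail delivery differ on any secondary outcome, although 30-day follow-up was explicitly wanted by group.

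**Working it through.** **1. Endpoints against the test.** Splitting the four groups gives seven measures.

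| Measure | What the protocol says | Paired binary data? |
|---|---|---|
| Health insurance | binary | yes, if asked at both interviews |
| Usual source of care | binary | yes, if asked at both interviews |
| Provider visit in six months | binary | only if also asked at intake, which is not shown |
| Knowledge score | continuous sum | no: not binary |
| 30-day follow-up | proportion per group, abnormal screens only | no: no baseline, independent arms |
| Knowledge of test results | scale not stated | very likely no baseline |
| Acceptability of delivery | scale not stated | very likely no baseline |

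The last two rows are inferred from section 14, where kits reach women after intake and results are phoned later. The survey itself is not in the documents. The count is 2 in conflict by wording, 2 very likely unsuited, and 3 suited (2 if provider visit was not asked at intake).

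**2. What the pooled test responds to.** The documents give no rates, retention or allocation ratio. Assume 1:1 allocation, 300 women per arm with both interviews, 50% with access at baseline, and 9% losing access. An arm changing by +6, +12 or -6 points then has 15%, 21% or 3% gaining access.

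- Pooled McNemar, N = 600: expected z is about N(gain - loss)/√[N(gain + loss)], using rates averaged over arms.
- Unadjusted six-month comparison: expected z is about (p2 - p1)/√[p1(1 - p1)/300 + p2(1 - p2)/300].

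| Change in the two arms | McNemar z | Six-month z | McNemar rejects | Between-arm test rejects |
|---|---|---|---|---|
| +6 / +6 | (90 - 54)/√144 = 3.00 | 0 (56% v 56%) | 86% | 5% |
| +6 / +12 | (108 - 54)/√162 = 4.24 | 0.06/0.0401 = 1.50 | 99% | 32% |
| -6 / +6 | (54 - 54)/√108 = 0 | 0.12/0.0405 = 2.96 | 5% | 84% |

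Rejection rates come from 20,000 simulated trials per setting, two-sided 5% level. For -6/+6, with 250 or 350 per arm, or with baselines of 30-70% and losses of 6-12%, McNemar stays at 5% and the between-arm test lies between 78% and 90%. A separate simulation with 350 per arm, testing the difference in change, agrees: 99.9% v 5.1% when both arms gain 10 points, and 4.6% v 99.9% when they move 10 points in opposite directions.

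**3. Precision of the missing estimates (assumed 250-350 per arm).**

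- *Access difference*, 1.96√[2p(1 - p)/n]: p = 0.3, n = 350 gives 6.8 points; p = 0.5, n = 250 gives 8.8 points. At n = 300, p = 0.5 it is 8.0, falling to about 6-7 with baseline adjustment.
- *Knowledge difference by ANCOVA*, 1.96√[2(1 - r²)/n] in SD units: r = 0.7, n = 350 gives 0.106; r = 0.3, n = 250 gives 0.167.
- *30-day follow-up*: assuming 350 per arm, 50-90% kit return and 8-20% abnormal, the subset is 350 × 0.5 × 0.08 = 14 to 350 × 0.9 × 0.20 = 63 women per arm. With about 80% followed up, the Wilson 95% interval is 52.4-92.4% (11/14) or 67.8-87.5% (50/63). The Newcombe interval for a zero arm difference is ±29.6 or ±14.1 points.

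**The case against.** The best defence is that most secondary aims are not about the arms. Access is meant to show whether self-sampling reduced it, and both arms self-sample. Knowledge is a fidelity check, and both arms receive education. A within-woman change suits both aims, and only 30-day follow-up is explicitly promised by group. The section 7 objective is met by the primary by-arm test. Further, the SAP never says it pools the arms and does not list which outcomes its sentence covers. If it meant only paired binary items, the fault is an omission rather than a wrong test. The simulation uses assumed rates and shows something true by definition.

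Part of this stands. McNemar is a fair description for the binary access items, and a between-arm model would not show whether self-sampling itself changed access. Pooling is inferred, though it is the natural reading of an overall-sample test stratified only by site, and no McNemar test on interview pairs compares the arms even if run within each arm. The numbers are illustrative.

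The rest does not rescue the plan. A within-woman aim for knowledge still needs a method for a continuous score. The narrower reading leaves four measures with no method at all. In a randomised comparison of two delivery modes, having no arm estimate for any secondary outcome is a real gap.

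**Conclusion.** The concern holds. The mismatch for the knowledge score and for 30-day follow-up rests on the documents' own wording, with no assumption about the survey. That for knowledge of results and acceptability is inferred. For access, the planned test is usable but uncontrolled and silent on the arm difference. That conclusion is structural; only the rejection rates and interval widths depend on the assumed inputs. The by-arm estimates for access and knowledge would be reasonably precise at the assumed sizes, and those for 30-day follow-up would be wide. The primary analysis of returned kits is not touched. This should be fixed, but it does not threaten the trial's main result.

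**What to change.** Give each secondary outcome its own method in the SAP.

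- **Knowledge score:** ANCOVA on arm, adjusted for baseline score and site, plus a paired test of continuous change as the fidelity check.
- **Access items:** keep McNemar, labelled an uncontrolled before-after description. Add a six-month arm difference with a 95% CI, adjusted for site and for the baseline value where it was measured. State that this difference does not answer whether self-sampling reduced access.
- **30-day follow-up:** proportion by arm among women with an abnormal screen, with the denominator and an exact or Wilson interval, labelled descriptive because the subset is formed after randomisation.
- **Knowledge of test results:** by arm, with the denominator stated.
- **Acceptability:** by arm only if collected in both arms. The kit paragraph in section 14 speaks of feedback from one arm.

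The cost is SAP wording and a few models. Interviews are planned at intake and six months in both arms, and section 17 says access and knowledge are asked about. Whether provider visit was asked at intake must be confirmed. The SAP is dated 2/2/17 and written in the past tense, so any added model first run after the data were examined should be labelled post hoc.
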